Physical, medical, and health-related quality of life changes following SCI: SCI results in paralysis and near permanent loss of voluntary function below the level of lesion. Those with more severe neurological lesions lose the ability to perform the weight bearing activities of standing and walking. Most become wheelchair users for indoor and outdoor mobility. The loss of the ability to walk is an obvious consequence of SCI. However, there are many less observable complications that result from loss of walking activity that serve to reduce quality of life (QOL), such as compromised bowel and bladder function, increased pain, extreme changes in body composition, and difficulty sleeping. On a daily basis, coping with loss of bowel [1-3] and bladder [4, 5] function, chronic pain [6], and difficulty sleeping [7] takes a tremendous, and often unrecognized, toll on emotional and physical well-being. Chronic constipation [8] and difficulty with evacuation are time consuming, taking hours per week, requiring prescription of multiple types of stool softeners and laxatives, and often the use of enemas and/or digital stimulation to perform a bowel evacuation, all of which are over-shadowed by the ever-present anxiety of a potential bowel accident [1, 9]. Standing alone has not been demonstrated to be effective in decreasing time to first stool for a bowel evacuation [10]. Constant sitting often leads to chronic back pain and, in those with some sensation below their lesion, leg pain is also prevalent [11]. Uncontrolled muscle spasms, which are similar to leg cramps in those who are not paralyzed, also cause discomfort and pain and may be severe at times [12]. Sleep is unremittingly interrupted due to spasms, pain and other conditions directly related to paralysis [7, 13, 14]. Immobilization from SCI has severe consequences on body composition [15-18]. Within the first two years after SCI, persons with motor-complete lesions may be expected to gain as much as 10 kg of total body fat mass and to lose a similar amount of lean tissue mass ([name], et.al., manuscript under review). With these

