Psychometric Properties of the SCI-QOL/SCI-FI: Each of the final SCI-QOL/SCI-FI item banks is a unidimensional set of items (determined by confirmatory factor analysis) that have been calibrated with item response theory (IRT). The stability of the IRT calibrations provides preliminary evidence of the SCI-QOL's validity [60]. Furthermore, all SCI-QOL banks demonstrate internal consistency (Cronbach's alpha) and 2-week test-retest reliability. Finally, the SCI-FI (physical functioning) banks have demonstrated responsiveness to the naturally occurring change following SCI at both 6 month and 1 year time points.

The PROMIS Sleep Disturbance outcome measure was validated and calibrated using classic validation techniques and IRT in more than 2,200 adults from an internet pooling sample and medical, psychiatric and sleep clinics [69, 70]. Moderate to high correlations were demonstrated between existing sleep scales and by statistically significant differences found between patients with known sleep disorders and those without any [69]. The PROMIS Sleep Disturbance outcome measurement was found to be sufficient because no unique questions that required SCI-specific content were thought to be needed [66]. The PROMIS Sleep disturbance outcome measure is a useful tool as is.

A clinically significant difference of the patient-reported outcomes for the QOL measurement determined from any of the PROMIS, Neuro-QOL, SCI-QOL, or SCI-FI assessment tools has been undergoing evaluation. In the interim, three prominent investigators in this field joined forces to determine a consensus of a clinically relevant change for any of these patient-reported outcome questionnaires [71]. These investigators support a ½ standard deviation (SD) as a conservative estimate for a clinically meaningful change. A minimally important difference (MID) is expected to be below a ½ SD. They report that, in lieu of a specifically tested effort to determine the MID in a specific population (such as SCI), use of the ½ SD is a strong and conservative approach [71].

In addition to a scientific rationale (please refer to the pilot data), there are ethical and financial considerations that support the justification for the VA to fund this initiative. It has been long recognized that a sedentary lifestyle is deleterious for one's health, self-esteem and well-being.

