Sample size/power calculation for the Primary Outcome (2) SCI-QOL for Bladder, Bowel and Pain: An improvement of 10% in the sum T-score of the patient-reported outcomes from the combined SCI-QOL item banks for bladder management difficulties, bowel management difficulties and pain interference is clinically significant. As such, it is hypothesized that 42% of the Intervention group compared with 10% of the Control group will demonstrate a clinically significant change of 10% improvement from baseline to the end of the intervention phase on the sum T-score in the combined SCI-QOL item banks for bladder management difficulties, bowel management difficulties and pain interference. (Table 7).

Sample size/power calculation for the Major Secondary Outcome for Total Body Fat Mass: Patients with a new SCI can be expected to gain an average of 6.0 ± 8.9 kg of fat mass in the first 14 months after injury (manuscript in preparation from our Center). This gain in fat mass appears to continue throughout the duration of their life after SCI. As demonstrated in the preliminary data, an intervention that supports a 1.0 kg (2.2 lb.) loss of fat mass is a substantial amount of fat mass to lose in three months for a person with SCI. Very few interventions have demonstrated changes in body composition of this magnitude in the SCI population. It is expected that 35% of the Intervention group compared with 10% of the Control group will maintain total body fat mass loss during the home/community use phase of the intervention.

Assuming the proportion in the control group achieving a clinically meaningful change to be 10% (or 0.100) for all three outcome measures, and estimating the attrition rate at 15%, the sample sizes range from a low of 71 per group (95% power) for the SCI-QOL PMH outcome to a high of 79 per group (80% power) for the MCS/VR-36 group. As a note about Table 7, to adjust for multiple outcome measures, a significance level of 0.025 was used in the sample size calculations for the co-primaries (MCS/VR-36 and SCI-QOL) and also for the major secondary outcome measure (Total Body Fat Mass). Based on the sample size and power calculations in Table 7, the study will enroll a total sample size of 160 participants, 80 per group.

Table 7: Sample Size/Power Calculations			
Two group continuity corrected χ^2 test of equal proportions (odds ratio = 1) (equal n's)	MCS/VR-36	SCI-QOL (PMH)	Total Body Fat Mass
Test significance level, α	0.025	0.025	0.025

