group will have a clinically meaningful change in the outcome measures for sample size/power calculations. Ten percent is thought to be a conservative estimate as there is no reason to expect the control group to have clinically meaningful changes in quality of life measures or in total body fat mass while continuing to receive SOC for their spinal cord injury. However, as a means of verifying the control proportion of 10% (or 0.100), the proportion of participants considered successful in the control group for all three outcomes and 95% confidence intervals for the proportions will be reviewed upon the completion of the feasibility phase. Based on the extensive experience with this population it is highly unlikely that the assumed success rates in the control group (SOC) will be any higher than the assumed 10%.

At the completion of the feasibility phase, the study will be moved to a continuation phase where the remaining sites (9 remaining sites) will be activated and the remaining participants will be recruited.

D. Baseline Comparability

Baseline comparability between the treatment groups will be evaluated with respect to such variables as demographics (e.g., age, gender, and race) and baseline values of outcome measures (MCS/VR-36, SCI-QOL, total body fat mass, etc.). Chi-square and analysis of variance techniques, as appropriate, will be used to determine any differences in distribution of the variables across the treatment groups. Any variable that appears to be different between the groups ($p < 0.10$) will be considered as a potential covariate in statistical analyses.

E. General Outcome Analysis Guidelines

All statistical tests will be 2-sided. The two primary and major secondary outcome measures will be tested at a 0.025 level of significance. Because of the large number of secondary outcomes to be analyzed, all other secondary outcomes will be tested at a significance level of 0.01 to maintain control over Type I error. SAS 9.4 will be used to conduct all the statistical analyses. A variety of analytic methods will be used for the primary endpoints, secondary endpoints and other analyses.

F. Analysis of Primary and Major Secondary Outcome Measures

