2. Interim time points of data collection for all outcome variables have been incorporated into the study design. These time points are: baseline, after training/orientation phase, two months into the intervention phase, and then again after four months of the intervention phase (primary and major secondary outcomes main time point). Secondary analyses of the MCS/VR-36, SCI-QOL, total body fat mass loss, Global Impression of Change and other secondary outcome measures will include comparisons of the mean difference scores (change from baseline to the end of each time point) of these outcome variables using t-tests. Other secondary analyses of outcome measures will be performed that use the all data available. For these continuous variables, repeated measures analysis of covariance will be used to analyze them, with baseline scores, plus any variables determined from the baseline comparisons, being used as covariates in the analyses. SAS MIXED and GENMOD procedures, which allow for the use of incomplete data sets, will be used if it can be safely assumed that missing data are missing at random. If this assumption is not valid, a multiple imputation strategy of the missing responses will be implemented which does not rely on the assumption that missing data occur at random. This will allow an intent-to-treat approach for the statistical analyses, where complete cases are not required.

3. An analysis to determine the characterization of the drop-outs will be performed by using descriptive and correlation statistics. The reasons for drop-out and the number of sessions/time points completed will be described. A correlation analysis will be performed with the reasons for drop-out and the demographic variables and other potential variables to identify characteristics of persons who drop out of the study.

H. Monitoring of Study by Study Group and Executive Committee

The Study Group (all of the Site Investigators) and Executive Committee will meet 6 to 9 months after patient recruitment begins and at annual intervals thereafter until the end of the study. Three weeks prior to these meetings and at 6-month intervals between the meetings, these groups will be provided a report that will allow them to assess study progress. Since both groups are composed of study participants, no outcome data will be provided in these reports. The information provided will include data on:

1. Screening, enrollment and retention
2. Patient background characteristics at entry

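### Time since injury is not a prespecified covariate in the supportive fat-mass ANCOVA, although the protocol's own figures suggest that it predicts fat change

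*Combined protocol and SAP*

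**What the plan says.** - **Natural course of fat mass.** The Introduction (section I) says that, in the two years after injury, "persons with motor-complete lesions may be expected to gain as much as 10 kg of total body fat mass". Section XIII.B, justifying the fat-mass endpoint, gives an average of 6.0 ± 8.9 "kg of fat mass in the first 14 months after injury" and adds: "This gain in fat mass appears to continue throughout the duration of their life after SCI". No later rate is given.
- **Entry.** Section VIII.A admits traumatic or non-traumatic injury of at least 6 months' duration, with no upper limit. Section VIII also admits both complete and incomplete lesions.
- **Randomization.** Section IV.B describes randomization within site. Time since injury is not mentioned as a stratifier.
- **Baseline comparison.** Section XIII.D compares the arms on variables such as "demographics (e.g., age, gender, and race) and baseline values of outcome measures". A variable that differs at p<0.10 becomes a potential covariate.
- **Continuous analyses.** Section XIII.G item 2 plans repeated-measures ANCOVA "with baseline scores, plus any variables determined from the baseline comparisons, being used as covariates in the analyses".
- **Main test for fat mass.** Section XIII.F compares the proportions losing at least 1 kg by an unadjusted chi-square test.

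**The concern.** By the protocol's own account, fat mass rises quickly early after injury. Someone entering at 8 months may be on a different trajectory from someone entering at 15 years. Baseline fat mass is in the model, but it measures the current level and not the current rate of change.

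A prognostic covariate earns its place because it predicts the outcome, not because the arms happen to differ on it. Under randomization, a p<0.10 screen leaves out a prognostic variable about 90% of the time, even if someone thinks to test it. It also leaves the model undefined until the data are seen. What is at stake is precision, and protection against a chance difference between arms in the number recently injured.

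**Working it through.** **1. The plan's own figure.** Table 7, total body fat mass: 10% v 35%, two-sided alpha 0.025, 85% power, continuity-corrected chi-square. Recomputed: 66 per group, and 66/(1 - 0.15) = 77.6, so 78 with attrition. Both match. This figure concerns the responder test and is not in dispute.

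**2. Early rate of gain (section I; XIII.B), taken as linear.** 10/24 = 0.42 kg/month and 6.0/14 = 0.43 kg/month.

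**3. Gain during the study.** Participation is 33 weeks (Executive Summary): 33/4.345 = 7.6 months. Then 0.417 × 7.6 = 3.2 kg and 0.429 × 7.6 = 3.3 kg. If baseline to final assessment is only 6.5 months, 0.417 × 6.5 = 2.7 kg. The success threshold is a loss of 1.0 kg.

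**4. Allowing for people who leave the two-year window.** Assume entry uniform over months 6-24 and 7 months between assessments. Entrants at months 6-17 spend all 7 months in the window. Entrants at months 17-24 spend 3.5 on average. Mean = (11 × 7 + 7 × 3.5)/18 = 5.6 months, or 2.3-2.4 kg.

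**5. Variance explained.** Let f be the share recently injured, c the difference in mean fat change between recent and long-injured participants, and SD the remaining standard deviation of change. Then R² = f(1 - f)c² / [SD² + f(1 - f)c²]. The documents give none of f, c or SD. I assume f = 10-30% and SD = 3-4 kg.

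| c (kg) | Basis | R², f = 0.1, SD 4 | R², f = 0.3, SD 3 |
|---|---|---|---|
| 3.16 | full early rate against no later gain | 5.3% | 18.9% |
| 2.4 | step 4 against no later gain | 3.1% | 11.8% |
| 1.5 | assumed, allowing for continued later gain | 1.2% | 5.0% |

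The equivalent increase in sample size is 1/(1 - R²) - 1. That is about 23% at R² = 18.9% and about 1% at R² = 1.2%.

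**6. What this means for power.** Illustration only: assumed mean difference 1.5 kg, f = 0.2, SD 3 kg, 80 per arm, two-sided alpha 0.025, noncentral t. Without the covariate, power is 74% (c = 3.16), 77% (c = 2.4) or 80% (c = 1.5). With it, power is about 81% in each case. The comparator here has no baseline-score adjustment, which the plan does have, so the gain over the planned model is not established.

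**7. Chance imbalance.** With f = 0.2, the standard error of the between-arm difference in the recent share is √(0.2 × 0.8 × 2/80) = 0.063. The 95% range is ±12 percentage points. Multiplied by c, this moves the mean difference by ±0.39 kg (c = 3.16), ±0.30 kg (2.4) or ±0.19 kg (1.5).

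**8. Type I error of the responder test.** Simulation (200,000 trials, 80 per arm, f = 0.1 to 0.3), supposing that no recently injured participant succeeds: the unadjusted chi-square rejects in 2.0-2.1% of null trials against a nominal 2.5%. There is no inflation.

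**The case against.** The strongest reply is that the plan already has a route to adjustment. The list in XIII.D is open, a variable flagged at p<0.10 passes to the ANCOVA, and XIII.I repeats the idea for participant characteristics. A reader might infer that the plan rules out adjustment for time since injury. It does not, and a marked imbalance could be handled. What stands is that the variable is unnamed and that the rule responds to imbalance, not to prognosis.

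A reader might also infer that the main fat-mass result is compromised. The documents do not support that. The efficacy test is the responder chi-square of XIII.F, which the proposed covariate does not touch. Natural gain acts on both randomized arms, so it does not bias their comparison. Even a stratified version of that test, under the extreme assumption in step 8, would gain only 0.5, 1.6 and 3.1 points of power at f = 0.1, 0.2 and 0.3.

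The drift may also be smaller than step 3 suggests. The 10 kg is an upper figure for motor-complete lesions, and the trial takes incomplete lesions too. Both rates average in the first six months after injury, when nobody is enrolled. Lifelong gain narrows the contrast with long-injured participants. All of this stands, and it is why the lower rows of the table matter.

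Finally, a reader might extend the point to SCI-FI, because section I.A says that "the SCI-FI (physical functioning) banks have demonstrated responsiveness to the naturally occurring change following SCI at both 6 month and 1 year time points". That sentence reports the instrument's responsiveness and gives no rate. SCI-FI is one of many exploratory secondary outcomes tested at 0.01. It supports an optional extension at most.

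**Conclusion.** The point holds as a modest, inexpensive improvement to the supportive continuous analyses of fat mass. The protocol supplies its own reason to regard time since injury as prognostic, opens entry at 6 months, and leaves the covariate to a data-driven screen. The loss is precision and protection against chance imbalance.

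The range of roughly 1-19% of variance rests on an assumed recent share of 10-30%, an assumed residual SD of 3-4 kg, linear early gain, and an assumed contrast of 1.5-3.16 kg. If few participants are recently injured, the gain is near zero and essentially nothing is lost by including the covariate. The power figures also depend on a 1.5 kg mean difference, which the protocol does not hypothesise.

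**What to change.** In XIII.G item 2, state that the repeated-measures ANCOVA for total body fat mass and abdominal fat mass includes time since injury (for example, log years at baseline) as a fixed, prespecified covariate, regardless of baseline imbalance. Extending this to SCI-FI is optional. Add time since injury to the variables named in XIII.D, so that its distribution by arm is reported.

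The cost is one degree of freedom and a sentence or two in the SAP. No new data are needed, because duration of injury must already be established for eligibility. The responder test in XIII.F and the sample size in Table 7 stay as they are.

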Table 1. SID=subject identification number; y=years; cm=centimeters; kg=kilograms; DOI=duration of injury; LOI=level of injury; AIS=American Spinal Injury International Standards Scale; LOA=level of assistance; s=seconds; m=meters; and NT=non-traumatic SCI. LOA was adapted from the FIM as one of the following: moderate assistance (Mod) – participant performs 50% to 74% of the task and the trainer has both hands on the participant or device at all times to provide occasional guidance or balance support; minimal assistance (Min) – the user performs 75% or more of the task and the trainer has one hand on the participant or device for infrequent guidance or balance support; supervision (S) – the trainer is not touching the participant but is close enough to reach in to provide support for balance or guidance as needed; and modified independence (MI) – the trainer does not provide any assistance, and the participant is fully independent while walking in device. Nineteen participants were consented for screening eligibility. Seven participants (SID#'s 2, 3, 4, 8, 12, 13, and 17) were screening failures: two for low BMD, one medical illness, and four for schedule conflicts.

Heart rate (HR) and blood pressure (BP): HR and BP responses were measured during each session in the resting seated position prior to standing and walking, immediately after walking while still standing and then again when seated, after the walking session. The results at 18±5 and 32±18 sessions are reported (Table 2). The vital sign responses during sitting and post walking were in the expected ranges, demonstrating an increase in HR from seated to walking. In the participants studied, there were no orthostatic hypotensive episodes with the postural changes from sitting to standing in the device.

Rating of perceived exertion (RPE): RPE is a self-reported indicator of how hard the person perceives that they are performing an activity. RPE correlates well with HR when a 0 is added to the rating value (for example, a RPE of 6 is equivalent to a HR of 60 bpm, a typical resting value; and a RPE of 20 is related to a maximal effort of a HR of 200 bpm [72, 73]. As the participants trained, more actual walking occurred during each session, yet their perception of exertion during walking was reduced (Table 2).

[figure not shown]
Sessions	RPE	Heart Rate (bpm)		SBP (mmHg)		DBP (mmHg)	
	Standing (post EAW)	Seated (pre EAW)	Standing (post EAW)	Seated (pre EAW)	Standing (post EAW)	Seated (pre EAW)	Standing (post EAW)
1 to 10	14±2	79±13	102±22	127±12	130±14	72±8	73±10
11 to 25	12±3	80±9	112±22	123±15	122±20	73±13	68±20
26 to 40	10±3	75±11	113±17	122±19	123±17	68±9	70±8
> 40	8±2	79±13	114±25	128±13	127±17	72±9	72±2

Table 2. SBP=Systolic blood pressure; DBP=Diastolic blood pressure; mmHg=millimeters of mercury; EAW=exoskeletal-assisted walking

C. Preliminary Data Employed for the Primary Outcome Variables

Primary Outcome 1 (supporting data): A commonly used measure of physical and mental patient-reported health outcomes is the SF-36 [74]. The SF-36 has been reported in persons with SCI of less than 6 months post injury [75] and in those who were less than four years post injury [76]. In the Veterans Health Administration, the Veterans Rand 36 (VR-36) has been used to document health-related QOL outcomes in Veterans [77-79]. The SF-36 was administered to participants before (N=12) and after (N=11, one lost to follow-up) EAW training. Using the MCS scores to calculate a mean difference and 95% CI for the upper and lower limits for the pre- and post- values, the average value for a net change demonstrated clinically significant improvement of 9.03 ± 17.02 , CI -2.4 to 20.5, $p=0.1087$ (Figure 4). **Four of 12 participants demonstrated a clinically relevant change of ≥ 4.0 on the MCS of the SF-36.** This proportion was used to calculate the power and sample size for the Primary Outcome 1 (MCS/VR-36) that is reported in the statistical section of the proposal. [Note, the MCS SF-36 was used for the preliminary study, but the MCS/VR-36 will be used in this study as the Primary Outcome 1.] In support of the average improvement in the MCS scores, comparisons were made with those of other studies where the SF-36 was administered to persons with SCI within 6 months of injury [75] and then in another group who were less than four years since injury [76]. The MCS average scores for the pre- and

post- ReWalk participants were compared to data from both studies. Lucke, et.al., who administered the SF-36 to persons with SCI of only 6 months duration [75] and Westgren et.al.

who administered the SF-36 in those with SCI of <4 years duration [76] (Figure 5). Both of these studies reported MCS scores of 51.8 and 51.9 respectively; the MCS scores from these prior reports are consistent with the findings of our 11 participants at baseline (MCS of 52.3). After EAW, the ReWalk participants increased to 61.5 (Figure 5).

Primary Outcome 2 (supporting data): Three item banks from the SCI-QOL Physical-Medical Health domain were used to assess pre- and post- changes after 40±15 sessions of exoskeletal-assisted walking in 11 participants (one of the 12 was lost to follow-

up for the QOL assessments). These item banks consisted of patient-reported outcomes for bladder

[figure not shown]
[figure not shown]

Figure 5. *SCI 6mo data from [64] vs. ReWalk Post; †SCI<4y [65] vs. ReWalk Post; ‡ReWalk Pre vs. Post.

management difficulties, bowel management difficulties, and pain interference. The group means for the pre-and post-values with the 95% CI are presented (Figure 6). Participants reported significant improvement (indicated as a reduction in scores) in the bladder (Figure 6A) and bowel (Figure 6B) item banks. Pain Interference also improved, but failed to reach statistical significance (Figure 6C). In

support of the SCI-QOL net pain improvements, analysis of the Physical Pain and Pain interference components from the SF-36 demonstrated significant net improvements from 50±24 to 76±12, p=0.0253. Using a simple sum score of the three SCI-QOL item banks (bladder, bowel and pain) from the Physical-Medical Health (PMH) domain, the mean difference from pre- to post-EAW training was -27.1±34.3; 95% CI: -50.1 to -4.0, p=0.0257. **Five of the 12 participants**

demonstrated a clinically relevant improvement of at least 10% in the sum score of the three item banks. This proportion, 42% responders, was used to calculate the power and sample size for the Primary Outcome 2 (PMH/SCI-QOL) that is reported in the Statistical Analysis Plan (Section XIII) of the protocol.

D. Supporting Data for the Major Secondary Outcome Variable

